9.4. Statistical Analyses

The statistical analysis plan (SAP) will be developed and finalized before database lock and will describe the subject populations to be included in the analyses, and procedures for accounting for missing, unused, and spurious data. This section is a summary of the planned statistical analyses of the primary and secondary endpoints. The SAP may modify the plans outlined in the protocol; however, any major modifications will also be reflected in a protocol amendment.

Since this is an open-label, single arm clinical study, descriptive summary statistics will be employed to analyze the data.

The standard summary statistics for continuous variables are sample size (n), mean, standard deviation, median, minimum and maximum. The standard summary statistics for categorical variables are frequencies and percentages. Time to event variables will be summarized using the Kaplan-Meier method. Where confidence limits are appropriate, the confidence level will be 95% (two-sided), unless otherwise stated. The only test of statistical significance will be performed according to the pre-defined analysis of the Simon 2-stage design.

Individual data (including relevant derived variables) will be presented by parameter in listings. Results of statistical analyses, descriptive summary statistics and supportive listings will also be presented.

Baseline values are defined as the last valid value prior to study drug administration. Baseline safety data will be presented along with subsequent safety values assessed during or after drug administration.

Statistical analyses will be performed using SAS® v9.4 or higher (SAS Institute, Cary NC, USA).

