9.4.3. Efficacy Analyses

Endpoint	Statistical Analysis Methods
Primary	
Primary efficacy analyses will be performed on ASaT Population.
 
The pCR will be estimated based on the proportion of subjects with no viable tumor on histologic assessment at definitive surgery. The estimated pCR will be accompanied by a 2-sided 95% exact binomial confidence interval (CI). Refer to statistical analysis plan (SAP) for detail.

Secondary	
DOR, PFS, iPFS, iBORR and OS (time to events endpoints) will be summarized descriptively using Kaplan-Meier methods. The censoring rules will be defined in the SAP. The ORR, BORR, and iBORR (categorical endpoints) will be summarized in a similar fashion as pCR. These will be assessed by Investigator based on Response Evaluation Criteria In Solid Tumors (RECIST) v1.1 at 12 weeks of Neoadjuvant phase (preoperative, unconfirmed). Refer to SAP for detail. Further, the risk of surgical delay (either due to toxicity and/or tumor progression) will be assessed. Surgery will be planned at about 12 weeks and any delays beyond the protocol allowed window will be monitored and reported.

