Complete Response (CR)¹	Disappearance of all target lesions, determined by two separate observations conducted not less than 4 weeks apart. Any pathological lymph nodes (whether target or non-target) must have reduction in short axis to <10 mm (the sum may not be "0" if there are target nodes). There can be no appearance of new lesions.	Disappearance of all non-target lesions and normalization of tumor marker level. All lymph nodes must be non-pathological in size (<10 mm short axis).
Partial Response (PR)¹	At least a 30% decrease in the sum of the longest diameter (LD) of target lesions, taking as reference the baseline sum LD. There can be no appearance of new lesions.	Non-target lesions must be non-PD.
Stable Disease (SD)	Neither sufficient shrinkage to qualify for PR nor sufficient increase to qualify for PD, taking as reference the smallest sum LD since the treatment started.	Persistence of one or more non-target lesion(s) and/or maintenance of tumor marker level above the normal limits.
Progressive Disease (PD)	At least a 20% increase in the sum of diameters of measured lesions taking as references the smallest sum of diameters recorded on study (including baseline) AND an absolute increase of ≥ 5 mm, or the appearance of one or more new lesions.	Appearance of one or more new lesions and/or unequivocal progression of existing non-target lesions.

¹ Subjects will meet the primary endpoint (BORR) if they attain a confirmed CR or PR over the 24 weeks with the combination treatment with a 4-week confirmatory scan per RECIST v1.1.

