10.7.1.1. Evaluation of Overall Response with RECIST v1.1

The overall response recorded from the start of the treatment until disease progression/recurrence (taking as reference for progressive disease the smallest measurements recorded since the treatment started). The subject's best response assignment will depend on the achievement of both measurement and confirmation criteria ([Table 6](#)).

Table 6 Overall Response Definitions using RECIST v1.1

Target Lesions	Non-Target Lesions	New Lesions	Overall Response	Best Response for this Category Also Requires
CR	CR	No	CR	Normalization of tumor markers, tumor nodes <10 mm
CR	Non-CR/ Non-PD	No	PR	
CR	Not all evaluated	No	PR	
PR	Non-PD / No all evaluated	No	PR	
SD	Non-PD	No	SD	Documented at least once ≥ 4 weeks from baseline
Not all evaluated	Non-PD	No	NE	
PD	Any	Any	PD	
Any	PD*	Any	PD	
Any	Any	Yes	PD	

* In exceptional circumstances, unequivocal progression in non-target lesions may be accepted as disease progression

Source: ([Seymour, 2017](#))

Other definitions

- Duration of response (DOR)
- Relapse free survival (RFS) – RFS is defined as the time, in months, from the first dosing date until the date of disease relapse (i.e., the date of the tumor imaging) or death from any cause. RECIST v1.1 will be used to determine the dates of relapse as this methodology is accepted by regulatory authorities. This will be further detailed in the SAP.
- Overall survival (OS) - OS is defined as the time from diagnosis until death from any cause. Subjects without a confirmed date of death will be censored at the last date when the subject was known to be alive.

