The event date to be used for calculation of progression-free survival (iPFS) should be the first date at which progression criteria are met (i.e., the date of iUPD) provided that iCPD is confirmed at the next assessment. If iUPD occurs, but is disregarded because of later iSD, iPR, or iCR, that iUPD date should not be used as the progression event date

Table 7 iRECIST Time Point response

Target Lesions*	Non-Target Lesions*	New Lesions*	Time Point Response	
			No prior iUPD**	Prior iUPD**; ***
iCR	iCR	No	iCR	iCR
iCR	Non-iCR/Non-iUPD	No	iPR	iPR
iPR	Non-iCR/Non-iUPD	No	iPR	iPR
iSD	Non-iCR/Non-iUPD	No	iSD	iSD
iUPD with no change OR decrease from last time point	iUPD with no change OR decrease from last TP	Yes	NA	New lesions (NL) confirms iCPD if NLs were previously identified and increase in size (≥ 5 mm in sum of measure (SOM) for new lesion, target (NLT) or any increase for new lesion, non-target; NLNT) or number. If no change in NLs (size or number) from last time point, remains iUPD
iSD	iUPD	No	iUPD	Remains iUPD unless iCPD confirmed based in further increase in size of non-target disease (need not meet RECIST v1.1 criteria for unequivocal PD)
iUPD	Non-iCR/Non-iUPD	No	iUPD	Remains iUPD unless iCPD confirmed based on: 
 ○ further increase in SOM of at least 5 mm, otherwise remains iUPD
iUPD	iUPD	No	iUPD	Remains iUPD unless iCPD confirmed based on further increase in: 
 ○ previously identified T lesion iUPD sum of measure ≥ 5 mm and / or ○ NT lesion iUPD (prior assessment - need not be unequivocal PD)
iUPD	iUPD	Yes	iUPD	Remains iUPD unless iCPD confirmed based on further increase in: 
 ● previously identified Target lesion iUPD ≥ 5 mm and / or ● previously identified non-target lesion iUPD (need not be unequivocal) and /or ● size or number of new lesions previously identified
Non-iUPD/PD	Non-iUPD/PD	Yes	iUPD	Remains iUPD unless iCPD confirmed based on

				○ increase in size or number of new lesions previously identified
--	--	--	--	---

TP = time-point; NT = non-target, T = target; NL = new lesions; iUPD = unconfirmed immune PD; iCPD = confirmed immune PD; SOM = sum of measures. iCR – immune complete response; iPR – immune partial response; iSD – immune stable disease

* Using RECIST v1.1 principles. If no PSPD occurs, RECIST v1.1 and iRECIST categories for CR, PR and SD would be the same.

** in any lesion category.

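### Section 9.4.3 does not match the listed secondary endpoints, and the removal sentence in 6.4.1 is at odds with the planned 5-year relapse and survival follow-up

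*Combined protocol and SAP*

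**What the plan says.** Sections 1.1 and 3 give the same secondary efficacy endpoints: ORR, DOR, RFS, iBORR (optional) and OS. RFS and OS are also named as objectives.

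Section 9.4.3 assigns the methods: "DOR, PFS, iPFS, iBORR and OS (time to events endpoints) will be summarized descriptively using Kaplan-Meier methods", and then "The ORR, BORR, and iBORR (categorical endpoints) will be summarized in a similar fashion as pCR". Section 9.4 has a general rule: "Time to event variables will be summarized using the Kaplan-Meier method". It allows a later SAP to change the plan, on condition that "any major modifications will also be reflected in a protocol amendment".

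Two appendix passages bear on the unlisted endpoints. The footnote to Table 5 (10.7.1) reads "Subjects will meet the primary endpoint (BORR) if they attain a confirmed CR or PR over the 24 weeks". Section 10.7.2 says "The event date to be used for calculation of progression-free survival (iPFS) should be the first date at which progression criteria are met".

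On follow-up, Section 1.1 plans survival contacts every 6 months for up to 5 years from registration. The 1.2 schema requires relapse and survival status in long-term follow-up, and 4.1 repeats the survival plan. The list of restricted therapies in 6.4.1 ends by saying that subjects who need any of them should leave the study. The same section closes by lifting all restrictions in post-treatment follow-up. Section 7.2 keeps two separate lists of reasons, one for ending participation and one for stopping medication.

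**The concern.** An analyst who builds tables from 9.4.3 would produce PFS, iPFS and BORR, which are not study endpoints, and would find no line for RFS, which is. iBORR would appear twice under two incompatible methods.

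The removal sentence raises a different matter. A subject who needs other systemic anticancer therapy while on study treatment is likely to be one in whom treatment is failing. If that subject leaves the study, survival status is lost just when the prognosis worsens. Censoring is then informative, and the Kaplan-Meier estimate drifts upward. OS is the more exposed endpoint. RFS is affected only where the other therapy starts before a relapse has been dated by RECIST.

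**Working it through.** **The plan's own figure.** The only design calculation is the Simon minimax rule in 9.2 (stop at 2 or fewer of 22; positive at 7 or more of 33; 10% against 30%). Exact two-stage binomial calculation gives a type I error of 0.041 and power of 0.902, in line with the stated 0.05 ceiling and 90%. The rule uses pCR only, so nothing below alters it.

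**Step 1: endpoint lists side by side.**

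| Endpoint | Listed in 1.1 and 3 | Method in 9.4.3 | Definition for this trial |
|---|---|---|---|
| ORR | yes | proportion | RECIST v1.1 at 12 weeks |
| DOR | yes | Kaplan-Meier | named in 10.7.1.1 |
| RFS | yes | none named | 10.7.1.1 |
| iBORR (optional) | yes | Kaplan-Meier and proportion | 10.7.2 |
| OS | yes | Kaplan-Meier | 10.7.1.1 |
| PFS | no | Kaplan-Meier | none |
| iPFS | no | Kaplan-Meier | event-date rule only, 10.7.2 |
| BORR | no | proportion | Table 5 footnote only |

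One listed endpoint is missing, three unlisted ones are present, and one is classed two ways. The footnote's label for BORR also contradicts 1.1, 3, 8.1.1 and 9.1, where the primary endpoint is pCR. Its confirmed response over 24 weeks does not fit a 12-week neoadjuvant phase with one planned post-baseline RECIST assessment before surgery (Schedule of Activities, note 5).

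**Step 2: follow-up wording side by side.**

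- 6.4.1 uses two ideas for the same situation. Earlier in the section, a clinical need for a prohibited medication may require stopping study therapy; the later sentence has the subject leave the study.
- 7.2 lists treatment failure as a reason to stop medication, not as a reason to end participation.
- Because restrictions end with treatment, a subject who first stops study drug and then starts other therapy stays in follow-up. One who needs the same therapy while still on treatment does not, if 6.4.1 is read literally.

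**Step 3: possible size for OS (illustration).** The document supplies N = 33 (9.2). The number removed *m*, landmark OS in the rest *s*, and landmark OS in those removed *s_r* are assumptions. Removal is taken to occur before any death in the rest.

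- With full follow-up: [(33 − m)·s + m·s_r] / 33
- With removed subjects censored early: s
- Overstatement: (m/33)·(s − s_r)

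Example, m = 3, s = 0.90, s_r = 0.50: full follow-up gives (30 × 0.90 + 3 × 0.50)/33 = 28.5/33 = 86.4%. Early censoring gives 90.0%. The difference is (3/33) × 0.40 = 3.6 points.

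Range for s from 0.85 to 0.95 and s_r from 0.60 to 0.40:

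| m | smallest (0.85 vs 0.60) | largest (0.95 vs 0.40) |
|---|---|---|
| 0 | 0 | 0 |
| 1 | 0.8 points | 1.7 points |
| 3 | 2.3 points | 5.0 points |
| 5 | 3.8 points | 8.3 points |

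Product-limit check: 4 of 33 leave at month 6, 2 of them die later, and 3 of the other 29 die between months 6 and 36. Full follow-up gives 28/33 = 0.848; removal gives 26/29 = 0.897, which is 4.8 points higher.

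These figures use a common time origin. Section 10.7.1.1 runs OS from diagnosis, and the illustration does not model the interval between diagnosis and enrolment.

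**The case against.** The best defence is that 9.4 calls itself a summary and sends the detail to a SAP due before database lock. RFS is listed, defined ("RFS is defined as the time, in months, from the first dosing date until the date of disease relapse") and covered by the general Kaplan-Meier sentence, so naming it in the SAP carries out the plan and need not be a major modification. That stands: a reader might infer that RFS has been dropped from the analysis, and the text does not support that. It does not rescue the list, which still names three endpoints the study does not have and puts iBORR under a method that does not suit a proportion.

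On 6.4.1, the defence is that sites may read leaving the study as leaving study treatment, that investigator request is an accepted exit in 7.2, and that most failing subjects will stop drug and pass into unrestricted follow-up. The last point stands and confines the problem to the treatment period. The first is not what the sentence says. The second would confirm the loss of data.

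Further inferences go beyond the documents:

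- That 7.1 ends follow-up at 30 days. Its next sentence points to the Schedule of Activities, where the matching column is the EOS/Early Discontinuation visit.
- That unresected subjects have no imaging. The Schedule gives standard-of-care imaging in long-term follow-up, and note 13 extends it to 5 years from study entry.
- That the unstated RFS rule for unresected subjects is an error. It is deferred in so many words: "The censoring rules will be defined in the SAP". It is a detail for the SAP.
- That only death, withdrawal of consent or study termination can end follow-up. Section 7.2 has other exits, including loss to follow-up.

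**Conclusion.** Both parts hold, and both are minor. The endpoint list in 9.4.3 is wrong as written, and so is the Table 5 footnote; this follows directly from comparing the sections and rests on no assumption. The removal sentence in 6.4.1 is inconsistent with the planned follow-up and with 7.2. Its effect depends on how sites apply it and on how many subjects are concerned, which the documents do not say and which may be none. Under the assumed rates the overstatement of OS runs from 0 to 8.3 points; that range shows direction and scale and is not an estimate for this trial. Only descriptive secondary endpoints are involved. A reader might take the footnote to mean that the primary endpoint is in doubt, but every operative section names pCR, and the primary analysis and the Simon rule are unaffected.

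**What to change.** (a) In 9.4.3, add RFS to the Kaplan-Meier endpoints and list iBORR only as a proportion. Either drop PFS, iPFS and BORR or label them as supportive analyses outside Section 3. Correct the Table 5 footnote so that it does not call BORR the primary endpoint.

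(b) Reconcile the removal sentence and the closing line of 6.4.1 with 1.1, 1.2, 4.1 and 7.2. The text should make clear that relapse and survival status continue to be collected for every treated subject who starts other therapy, unless consent is withdrawn, the subject is lost to follow-up or the study ends. This concerns data collection only; no treatment rule is proposed.

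The cost is wording. The six-monthly contacts are already planned, and the disposition summary in 9.4.1 will show whether anyone was removed. OS or RFS figures may come out slightly less favourable.

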Definitive Surgery Phase: Surgery may be scheduled about 2-4 weeks after the last dose of nivolumab following radiologic and clinical assessment at that point. Pathologic response will be determined by institutional pathologist. Under certain circumstances, the definitive surgery may be delayed and done after completion of additional cycles of neoadjuvant therapy if decided by the treating physician investigators (surgeon and medical oncologist) to be in the best interest of the patient (or can be done earlier if study intervention(s) was discontinued due to AEs or other reasons).

Adjuvant Phase: Adjuvant therapy with nivolumab monotherapy will begin approximately 2-4 weeks following definitive surgery, but can be later as clinically indicated to allow medical clearance for systemic therapy; recovery from surgery is required (Day 1 of Cycle 4 will be determined by the treating investigator once the subject is cleared to initiate systemic therapy). Nivolumab (480 mg IV infusion on Day 1 of each 4-week cycle) will be administered for up to 9 cycles during the Adjuvant phase.

Follow up:

- All subjects will be followed for 4 weeks after last dose of nivolumab at End of Study (EOS) visit.
- In the absence of disease progression, data from standard of care imaging will be captured every 3 months for 2 years post-surgery and every 6 months thereafter for up to 3 years post-surgery.
- Long-term survival status will be performed every 6 months (by phone) for up to 5 years from study registration, unless the study is terminated early.

Protocol Monitoring Committee (PMC) review: Moffitt PMC will monitor safety and efficacy parameters as specified in the PMC section later in this protocol.

Disclosure Statement: This is a single group treatment study with 1 arm that has no masking.

Number of Subjects: Up to 33 subjects; in Simon minimax Stage 1, up to 22 subjects can be enrolled. If the number of pCR in Stage 1 meet the pre-specified number ($N \geq 3 / 22$), enrollment for Stage 2 will include an additional 11 subjects (for a total of 33 subjects).

Study Duration: For each subject, the total duration of study participation will be 1 year (excluding the Screening period), plus long-term follow-up of up to 5 years (until death, subject withdraws consent or the study was terminated):

- Screening period: up to 4 weeks
- Neoadjuvant phase: 12 weeks (Up to 3 x 4-week cycles)
- Definitive surgery phase: approximately 2-4 weeks

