1.2. Schema

Neoadjuvant

Phase

(Up to 3 x4-week cycles;
12 weeks)

- Intra-tumoral TAVO-EP on Days 1, 8 and 15 (optional) of each 4-week cycle.
- Nivolumab 480 mg IV infusion on Day 8 of each 4-week cycle.
- On Day 8, TAVO-EP will be administered prior to nivolumab infusion.

Definitive Surgery

Phase

- Surgery approximately 2-4 weeks after the last dose of nivolumab.
- Pathologic response will be determined by the institutional pathologist.
- Surgery may be done sooner or delayed if clinically indicated based on disease status and recovery from adverse events as determined by the treating physician investigator to be in the patient's best interest.

Adjuvant

Phase

(Up to 9 x4-week cycles)

- Recovery from surgery is required (Cycle 4 Day 1 is determined by the treating physician investigator once the patient is cleared to initiate adjuvant systemic therapy; Approximately 2-4 weeks following definitive surgery but can be later as clinically indicated to allow medical clearance for systemic therapy).
- Nivolumab 480 mg IV infusion on Day 1 of every 4-week adjuvant cycle, up to 9 cycles.

Follow-Up

Phase

- Subjects will follow up 4 weeks after the last dose of nivolumab (End of Study visit).
- Long term follow-up in accordance with the standard of care.
- Long term follow-up status either in clinic or via phone, but must collect information on disease status (relapse or not) and survival.

NOTE: At the discretion of the treating physician investigator and as discussed with the patient as a means of maximizing local effects of tavo, an optional additional cycle of tavo-EP can be administered during the 3rd week (Day 15) of each of the 3 neoadjuvant cycles in the absence of limiting toxicities.

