3. OBJECTIVES AND ENDPOINTS

Objectives	Endpoints
Primary	

 To assess the complete pCR of intratumoral tavo-EP in combination with IV nivolumab (collectively 'the combined treatment') in subjects with operable locally-regionally advanced melanoma. 	
 pCR defined as proportion of subjects with no viable tumor on histologic assessment at definitive surgery.
Secondary	

 To assess 
 (a) radiologic/clinical preoperative response rate, (b) RFS and (c) OS. 	
 ORR assessed by Investigator based on RECIST v1.1 at 12 weeks during the Neoadjuvant phase (preoperative, unconfirmed). Duration of response (DOR) RFS iBORR assessed by Investigator based on iRECIST (optional). OS

 To assess safety and tolerability of the combined treatment as neoadjuvant therapy in subjects with operable locally-regionally advanced melanoma. 	
 Frequency, duration and severity of AEs and SAEs. Number of subjects with ECIs. Number of subjects who discontinued due to AEs. Incidence and shifts of clinically significant laboratory abnormalities; safety laboratory evaluations includes CBC, blood biochemistry and urinalysis.

 To assess the risk of surgical delay (either due to toxicity and/or tumor progression). 	
 Definitive surgery will be planned at about 12 weeks. Patients will be monitored for surgical delay (either due to toxicity and/or tumor progression).
Exploratory	

 Immune monitoring. 	
 Characterization of the tumor microenvironment and assessment of

Objectives	Endpoints
	immune phenotypes and function associated with treatment

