4. STUDY DESIGN

4.1. Overall Design

This will be a Phase 2, Simon 2 stage minimax, open-label, single-arm study of neoadjuvant treatment of intratumoral tavo-EP plus nivolumab IV. Eligible subjects will be those with pathological diagnosis of operable locally-regionally advanced melanoma. The purpose and procedures of the study will be fully explained to potential subjects. Those wishing to enroll in the study will sign a written informed consent prior to initiating any study-related evaluations or procedures. Screening must be completed within 28 days prior to initiation of the study treatment (i.e. Cycle 1 Day 1; C1D1).

The Treatment period will be comprised of 3 phases:

Neoadjuvant Phase (Up to 3 x 4-week cycles, total 12 weeks): At every cycle, intratumoral tavo-EP will be administered (on Days 1 and 8) concurrently with 480 mg nivolumab IV infusion on Day 8 of each cycle (tavo-EP will be administered prior to nivolumab infusion).

Definitive Surgery Phase: Surgery may be scheduled about 2-4 weeks after the last dose of nivolumab following radiologic and clinical assessment at that point. Pathologic response will be determined by institutional pathologist. Refer to Appendix 8 (Section 10.8) for suggested guidelines on surgical management and techniques. These are important standard of care surgical guidelines and all investigators are strongly urged to consider them in the management of their patients. Under certain circumstances, the definitive surgery may be delayed and done after completion of additional cycles of neoadjuvant therapy if perceived by the treating physician investigators (surgeon and medical oncologist) to be in the best interest of the patient (or earlier if study intervention(s) was discontinued due to AEs or other reasons).

Adjuvant Phase: Adjuvant therapy with nivolumab monotherapy will begin approximately 2-4 weeks following definitive surgery; recovery from surgery is required (Day 1 of Cycle 4 will be determined by the treating investigator once the subject is cleared to initiate systemic therapy). Nivolumab (480 mg IV infusion on Day 1 of each 4-week cycle) will be administered for up to 9 cycles during the Adjuvant phase.

In Simon minimax Stage 1, up to 22 subjects can be enrolled. If the number of responders in Stage 1 meet the pre-specified number ($N \geq 3 // 22$), enrollment for Stage 2 will include an additional 11 subjects (for a total of 33 subjects).

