6.6.2. Nivolumab

It is recommended to continue treatment with nivolumab for clinically stable subjects with initial evidence of disease progression until disease progression is confirmed.

Dose escalation or reduction is not recommended. Dosing delay or discontinuation may be required based on individual safety and tolerability. Guidelines for permanent discontinuation or withholding of doses are described in [Table 1](#). Detailed guidelines for the management of immune-related adverse reactions are described in Nivolumab package insert.

If during the neoadjuvant phase, nivolumab is withheld or discontinued, tavo-EP can be administered as monotherapy (up to 3 4-week cycles) after discussion with principal investigator.

Table 1 Recommended treatment modifications for nivolumab

Immune-related adverse reaction	Severity	Treatment modification
Immune-related pneumonitis	Grade 2 pneumonitis	Withhold dose(s) until symptoms resolve, radiographic abnormalities improve, and management with corticosteroids is complete
	Grade 3 or 4 pneumonitis	Permanently discontinue treatment
Immune-related colitis	Grade 2 diarrhea or colitis	Withhold dose(s) until symptoms resolve and management with corticosteroids, if needed, is complete
	Grade 3 diarrhea or colitis	Withhold dose(s) until symptoms resolve and management with corticosteroids is complete
	Grade 4 diarrhea or colitis	Permanently discontinue treatment
Immune-related hepatitis	Grade 2 elevation in aspartate aminotransferase (AST), alanine aminotransferase (ALT), or total bilirubin	Withhold dose(s) until laboratory values return to baseline and management with corticosteroids, if needed, is complete
	Grade 3 or 4 elevation in AST, ALT, or total bilirubin	Permanently discontinue treatment
Immune-related nephritis and renal dysfunction	Grade 2 or 3 creatinine elevation	Withhold dose(s) until creatinine returns to baseline and management with corticosteroids is complete
	Grade 4 creatinine elevation	Permanently discontinue treatment

Immune-related adverse reaction	Severity	Treatment modification
Immune-related endocrinopathies	Symptomatic Grade 2 or 3 hypothyroidism, hyperthyroidism, hypophysitis, Grade 2 adrenal insufficiency Grade 3 diabetes	Withhold dose(s) until symptoms resolve and management with corticosteroids (if needed for symptoms of acute inflammation) is complete. Treatment should be continued in the presence of hormone replacement therapy ^a as long as no symptoms are present

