10.7.1. RECIST v1.1

Tumor response will be evaluated according to RECIST guidelines ([Therasse, 2000](#)) using tumor imaging (see [Section 10.7.3](#) for tumor imaging details).

Assessment by RECIST v1.1 will be done as specified in the SoA. If during the neoadjuvant phase, a treatment delay results in shifting cycles, imaging and tumor evaluation will be shifted accordingly. Lesions will be numbered identically for each visit as Target and non-target, new lesions (see definitions in [Table 8](#)).

In support of RECIST v1.1, when more than one accessible and measurable tumor is present at baseline, all lesions (those with the longest diameter(s)/ organ that are measurable in the physicians' discretion) up to 2 cutaneous lesions assessed by photography and up to 5 visceral or subcutaneous lesions (2 per organ), assessed by radiology, with a maximum of 7 lesions total should be identified as measurable representative Target Lesions. A target lesion may be a treated or untreated lesion.

An 'accessible lesion' is defined as a cutaneous or subcutaneous lesion that can be reached from the surface with the electroporation needle array (with depth of up to 1.5 cm from the surface). Measurable lesions include non-lymph node longest axis ≥ 10 mm (on CT, PET-CT, MRI, or calipers/rulers), non-lymph node longest axis ≥ 20 mm (on X-ray) and lymph node short axis ≥ 15 mm. All lesions will be indicated by pen and numbered before being photographed. This provides the baseline map of ALL accessible lesions with baseline defined as the period between signing the ICF and prior to completion of Cycle 1. Each lesion will be identified by a lesion number which must remain the same throughout the study. Measurable lesions that are target lesions must be measured by the site and data entered into electronic data capture (EDC).

Each subject will be assigned a response category ([Table 5](#)): complete response (CR), partial response (PR), stable disease (SD), progressive disease (PD).

Preoperative response rate (unconfirmed) will be assessed during the Neoadjuvant phase (preoperative, unconfirmed).

Table 5 Response Evaluation Criteria in Solid Tumors v1.1

RECIST v1.1 Response Criteria	Target Lesions	Non-Target Lesions

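### Do the two stated surgery timings and the 30-day event period leave the surgical-delay endpoint unworkable?

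*Combined protocol and SAP*

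**What the plan says.** Section 3 makes the risk of surgical delay, whether from toxicity or progression, a secondary objective and adds: "Definitive surgery will be planned at about 12 weeks". Section 9.4.3 carries this into the analysis: "Surgery will be planned at about 12 weeks and any delays beyond the protocol allowed window will be monitored and reported". Section 10.3.3 also lists a delay of definitive surgery past the permitted windows as an event of clinical interest (ECI), so it enters a second secondary endpoint in Section 3, "Number of subjects with ECIs".

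The design sections tie surgery to nivolumab instead. The Synopsis has "Surgery may be scheduled about 2-4 weeks after the last dose of nivolumab", the Schema has "Surgery approximately 2-4 weeks after the last dose of nivolumab", and Section 4.1 has "Surgery may be scheduled about 2-4 weeks after the last dose of nivolumab following radiologic and clinical assessment at that point". Sections 1.1, 1.2, 4.1 and 10.8 then allow surgery to be earlier or later, including after extra neoadjuvant cycles.

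Three other rules bear on subjects who leave the schedule:
- Section 6.6.2 says that if, in the neoadjuvant phase, "nivolumab is withheld or discontinued, tavo-EP can be administered as monotherapy (up to 3 4-week cycles".
- Section 10.7.1 says: "If during the neoadjuvant phase, a treatment delay results in shifting cycles, imaging and tumor evaluation will be shifted accordingly".
- Table 3 in Section 8.3.1 ends ECI reporting 30 days after the last study dose, or 30 days after new anti-cancer therapy starts if that is earlier.

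The notes to Section 1.3 give one extra week for rescheduling treatment and procedures, without saying whether surgery is included. Section 9.4 defers detail to a SAP to be finalised before database lock.

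**The concern.** The endpoint counts delays against a window that is not named, and two timings could serve as its reference. Toxicity is what stops nivolumab or shifts cycles, so the subjects for whom the two timings part are the ones the objective is about. One subject could be counted as delayed on one reading and on time on the other.

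The ECI rule adds a second difficulty. If reporting closes before a delay can be recognised, a delay that Section 10.3.3 calls an ECI falls outside Table 3, and the ECI count and the delay count could differ for the same subject. At stake are two descriptive secondary counts. The primary pCR analysis does not depend on either.

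**Working it through.** **Inputs.** Cycles last 28 days, with up to three neoadjuvant cycles and nivolumab on Day 8 of each (Section 4.1). Surgery is at about 12 weeks (Sections 3 and 9.4.3), or 14-28 days after last nivolumab (Sections 1.1, 1.2 and 4.1). ECI reporting ends at last dose + 30 days (Table 3). *Assumption:* 12 weeks is counted from Cycle 1 Day 1 as day 1, so it falls on day 84 + 1 = 85. The documents give no origin and no tolerance.

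**Formula.** Last nivolumab in cycle k is on day 28(k − 1) + 8, that is day 8, 36 or 64. The nivolumab interval is that day + 14 to + 28.

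| Course | Last nivolumab | Interval | Surgery | Against day 85 | Against interval |
|---|---|---|---|---|---|
| On schedule | 64 | 78-92 | 85 | on time | on time |
| Nivolumab stops after cycle 1 | 8 | 22-36 | 85 | on time | 85 − 36 = 49 days past |
| Nivolumab stops after cycle 2 | 36 | 50-64 | 85 | on time | 85 − 64 = 21 days past |
| Cycles shifted 28 days | 92 | 106-120 | 106-120 | 21 to 35 days past | on time |

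The on-schedule row reproduces the plan's own figure: (78 − 1)/7 = 11.0 and (92 − 1)/7 = 13.0 weeks, which brackets 12.

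**Tolerance on week 12 (assumed).** One week gives day 92 and two weeks day 99. The 28-day shift starts at day 106 and stays late under both. A 14-day slip with surgery 21 days after nivolumab falls on day 78 + 21 = 99, which is late with one week and on time with two. So the smaller disagreements depend on how the word about is read.

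**Reading of Section 6.6.2.** The cycle 1 and 2 rows take the three tavo-EP cycles as a total. If three further cycles after cycle 1 were meant, tavo-EP would reach cycle 4 Day 8 = 28 × 3 + 8 = day 92, and surgery on day 85 would fall during treatment.

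**ECI period, no further dose.**
- *Nivolumab reference:* a delay first counts on day 29 after the last dose and reporting ends on day 30, so reporting does not close first. If the extra week applied to surgery, the interval would run to day 35 and reporting would end 35 − 30 = 5 days before it closed.
- *Week 12 reference:* last dose on day 8 or 36 gives closure on day 38 or 66, which is 85 − 38 = 47 or 85 − 66 = 19 days before week 12. With optional Day 15 tavo-EP as the last dose (day 15 or 43), closure is day 45 or 73, which is 40 or 12 days before.

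**Do the two problems meet?** A subject who continues tavo-EP alone to cycle 3 Day 8 or Day 15 (day 64 or 71) has ECI cover to day 94 or 101, past day 85. A subject who goes on to adjuvant nivolumab has a later last dose and so a later closure. The gap before week 12 is confined to those who stop all dosing early (or start new anti-cancer therapy).

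**Weight of one subject.** 1/33 = 3.0 and 1/22 = 4.5 percentage points.

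**The case for a change.** The best case for a change runs as follows. One can read 12 weeks as the plan and the nivolumab interval as the window around it, but the protocol never says so. On that reading a toxicity that shifts nivolumab moves the window with it, so the slip never counts as a delay, although delay from toxicity is the stated objective. A SAP can choose a counting rule, but it cannot alter Table 3 or Section 10.3.3, which are protocol reporting rules with a 24-hour timeline.

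Part of this stands. The window is undefined in the legible text, although the schedule table in Section 1.3 is damaged in extraction and its entries for the surgery columns cannot be read. The SAP author will have to state which window was used.

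The rest carries less weight. Section 9.4.3 itself separates a planned time from an allowed window, and the only interval the text gives for surgery is the nivolumab one, so the plan-and-window reading is natural and consistent on schedule. A slip hidden by a moving window would still show in the time from first dose to surgery. Surgery carried out at the planned time is not a delay caused by toxicity merely because nivolumab ended sooner. The early-stop cases hold week 12 fixed, whereas Sections 1.1 and 4.1 allow earlier surgery after discontinuation. Sections 3 and 9.4.3 monitor delay independently of ECI reporting, so a delay outside Table 3 need not be lost.

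**Conclusion.** No change to the plan is called for. This is missing detail in a descriptive, untested secondary endpoint, and analysts can fill it sensibly by naming the counting window in the SAP. The disagreement is real but conditional: none on schedule, 49 or 21 days one way after an early nivolumab stop, and 21 to 35 days the other way after a 4-week shift. The number of subjects affected is not given and may be zero.

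Rewording would now gain little. The July 2023 note in Section 1.3 says all patients have completed the neoadjuvant phase and that the supporting company can no longer support the study. Section 9.4 already provides for individual listings, Section 9.4.1 for an account of protocol violations, and Section 6.3 for recording of dosing deviations, so any stated window can be applied to the data afterwards.

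This rests on three assumptions: dose and surgery dates are on record, 12 weeks runs from Cycle 1 Day 1, and the three tavo-EP cycles in Section 6.6.2 are a total. Nothing here says when surgery should take place.
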